### 4.2 Study Outcome Measures

The efficiency of various drop aids will be measured through the subject’s glaucoma progression at the end of the study. On the day of enrollment, the subject’s IOP and visual acuity will be measured as part of their standard of care exam. This information is recorded as the baseline exam, and will be compared to measure the patient’s glaucoma progression at the end of the study. Subjects will be required to record the date on which they began each of their glaucoma eye drop bottles, and the date each bottle was finished in a study diary provided by the research team. Subject’s satisfaction will be measured through a brief satisfaction survey approximately 3 weeks after their enrollment. After at least 6 weeks of study participation, subject will be followed up with their regularly scheduled glaucoma provider where they will fill out a second brief satisfaction survey. The study diary will be collected and a routine eye exam will be conducted, with their IOP checked as part of a standard of care clinic visit.

All surveys were created by a member of the research team. The satisfaction survey includes five questions to assess the precision of the drop aid device, overall patient satisfaction, and willingness to use the device long term. The questions are multiple choice questions in which the patient circles the answer that best reflects their response.

Reference Section 12.0 for further statistical analysis explanations.

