### 5 Study Design

This interventional clinical trial is a prospective, single center, randomized controlled study. Patients being treated for their glaucoma at BMC's Yawkey Eye Clinic will be selected. Patients will be randomly placed, without manipulations by the principle investigator or any member of the research team, on one of the drop aid devices (including Fabrication Autodrop Eye Drop Guide, Simply Touch Eye Drop Applicator, Owen Mumford OP 6100 Autosqueeze), in addition to a no drop aid control, for a total of 4 groups.

Subjects have an equal chance of being randomized to one of the following study arms:

- Arm A: No intervention – Control
- Arm B: Active Comparator- Eye Drop Aids Including:
  - Simply Touch Eye Drop Applicator
  - Fabrication Autodrop Eye Drop Guide
  - Owen Mumford OP 6100 Autosqueeze

The primary endpoint is the comparison of baseline IOP measurement and follow-up IOP measurement. This comparison will determine the efficacy of using a drop aid. The secondary endpoints include the precision of the drop aid, patient satisfaction, and their likelihood to use a drop aid outside of the study. Data collection for assessment of study objectives will be obtained via standard of care clinic visits and completion of study diary and satisfaction survey by the patient with assistance of research team, if needed.

See the Appendix section 15.1 for a schematic of the study design and section 15.3 for drop aid labels and instructions.

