### 9.1 Screening and Consent

Glaucoma ophthalmology patients who are thought to be eligible for the study based on the eligibility criteria and review of their medical record by the investigator and/or designated study team member will be approached about study participation. The patient's provider (who could be an investigator) will introduce the study to the patient. The provider will alert the investigator (if they are not already an investigator) and/or the designated study team member to assist with enrollment. The following will then be completed by the investigator and/or the designated study team member:

- Review of study inclusion/exclusion criteria
- The consent form will be reviewed with the patient and all study related questions will be answered in a private exam room or consult room.
  - Both the patient and the investigator or the designated study team member conducting the consent form will sign

- The patient will be sent home with a copy of the fully executed consent form
- The patient will also be given the contact information of the principal investigator, clinical research coordinator, and 24-hour emergency number as listed below:

[name]  
Principal Investigator  
[[contact]](mailto:[contact])  
[contact]

[name]  
Clinical Research Coordinator  
[[contact]](mailto:[contact])  
[contact]

BMC Department of Ophthalmology  
Emergency after Hours  
[contact], dial 0 for operator, and ask for on-call ophthalmologist

- Study-specific review of medical record and demographics

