### 9.3.2 Final Study Visit: At least 6 Weeks after Enrollment (SOC Clinic Visit)

- Subject will complete a satisfaction survey in person
- Subject's study diary will be collected
- Routine eye exam will be conducted
  - IOP and VA will be checked as part of SOC clinic visit
- Study participation is complete

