15.2.3 Home Study Diary

**Individual(s) completing this form:**  Study Subject  Research team member: \_\_\_\_\_ (initials)

**Date of completion:** \_\_\_\_\_

Study ID	
Medication Name: _____	Start Date: _____  End Date: _____
Medication Name: _____	Start Date: _____  End Date: _____
Medication Name: _____	Start Date: _____  End Date: _____

*Please complete this paper and bring it to your next eye appointment along with your drop aid and eye drops*

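### Nothing in the plan keeps the assigned arm from the person who reads the follow-up IOP, the primary endpoint

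*Combined protocol and SAP*

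**What the plan says.** Section 5 (Study Design) sets the endpoint: "The primary endpoint is the comparison of baseline IOP measurement and follow-up IOP measurement".

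For the final visit, section 9.3.2 lists these items in this order:
- "Subject will complete a satisfaction survey in person"
- "Subject's study diary will be collected"
- a routine eye exam, in which "IOP and VA will be checked as part of SOC clinic visit"

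Section 4.2 narrates the visit in the same order: "subject will be followed up with their regularly scheduled glaucoma provider where they will fill out a second brief satisfaction survey", followed by the diary and the exam.

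The footer of the Home Study Diary (15.2.3) instructs the patient: "Please complete this paper and bring it to your next eye appointment along with your drop aid and eye drops".

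The Satisfaction Survey (15.2.4) offers, on four of its five questions, a response for patients who have no drop aid. The form has a line for the study team member who completes it.

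Section 9.1 says that the patient's "provider (who could be an investigator) will introduce the study to the patient".

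The Schedule of Events (15.1, Table 1) puts the IOP check in the screening and consent column and the six-week column. Its row stands above the survey and diary rows. Section 9.2 also lists the baseline IOP ahead of randomisation.

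No section names the IOP reader or the tonometer, provides for masking that reader, or requires IOP to be taken before the survey is given or the device is seen.

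**The concern.** Patients cannot be masked to whether they hold a device, and the control arm has no sham. The person reading IOP could be masked, and the plan does not use that option.

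The two IOP readings are not equally exposed. The baseline reading is listed before assignment exists, so knowledge of the arm cannot affect it. The follow-up reading is taken when the arm may be known from the survey answers, from the device the patient has been asked to bring, or because the provider is an investigator. Any reader expectation would therefore fall on the follow-up value alone and pass in full into the change score. Randomisation balances patient characteristics but does not remove an error that depends on knowing the arm. With 40 patients, such an error could not be told apart from a device effect.

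**Working it through.** **1. Does any rule protect the reading?**

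| Source | What it lists | Bearing on the IOP reader |
|---|---|---|
| 9.3.2 | Survey, diary, then exam with IOP | Arm-revealing survey listed before IOP |
| 4.2 | Same order in narrative | Same |
| 15.1, Table 1 | IOP row above survey and diary rows | Opposite listing, so the order is not fixed |
| 15.2.4 | Response for patients with no drop aid | Answers separate control from device |
| 15.2.3 | Medication names and dates, no device field | The diary page does not reveal the arm; its instruction to bring the device can |
| 9.1 | Provider may be an investigator | Reader and study team are not kept apart |
| 9.2 and 15.1 | IOP listed before randomisation | Baseline protected by timing |

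None of these sets IOP ahead of the revealing steps, and none withholds the assignment from the reader.

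**2. The plan's own figure.** Section 12.2 gives ten patients in each of four groups: 4 × 10 = 40, as stated, which is 10 control and 30 device. The number was set by budget. Sections 12.2 and 12.3 give no alpha, power, effect size or SD, so there is no power calculation to reproduce.

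**3. Illustration of what a reader shift could do.** All of the following are assumptions: two-sided 5%; SD of IOP change 3 mmHg (range 2 to 4); no true device effect; no other change from baseline; an average reader shift b in the device patients' follow-up values.

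*Device v control, two-sample t-test (30 v 10).*
SE = SD × √(1/10 + 1/30) = 3 × 0.365 = 1.10 mmHg, df = 38, critical value 2.02. The non-centrality is b/SE, and the rejection probability comes from the non-central t distribution.

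| b (mmHg) | b/SE | False-positive rate, SD 3 |
|---|---|---|
| 0 | 0 | 5% |
| 0.25 | 0.23 | 5.6% |
| 0.5 | 0.46 | 7.3% |
| 1.0 | 0.91 | 14.4% |
| 1.5 | 1.37 | 26.6% |

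For b = 1.0 mmHg, the rate is 26.6% with SD 2 and 10.2% with SD 4.

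*Paired t-test, the method section 12.3 names as primary.* The non-centrality is b√n/SD. For b = 1.0 mmHg and SD 3:
- one device group, n = 10: 1 × √10/3 = 1.05, df 9, rate 15.7% (29.3% with SD 2, 10.9% with SD 4)
- pooled device patients, n = 30: 1 × √30/3 = 1.83, df 29, rate 42.3% (75.4% with SD 2, 26.3% with SD 4)

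With b = 0, each test returns to its nominal 5%. The fix does not change the 40 patients.

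**The case against.** Five objections carry weight.

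- **The order.** A reader might infer that the protocol requires the survey and diary before the eye exam. It does not. The items in 9.3.2 are a list, neither 9.3.2 nor 4.2 makes the order binding, and Table 1 lists IOP first. What stands is that no rule puts IOP ahead of the revealing steps. The device is also brought to the visit whatever the order.
- **The measurement.** A reader might infer that IOP here is a subjective, observer-read value. The documents name neither instrument nor reader, so this cannot be established. How far expectation can move a reading depends on the method. That leaves the size of any bias uncertain but does not show that the endpoint is protected.
- **The routes.** The diary page has no device field, so collecting it does not unmask anyone. Nor do the documents say that the IOP reader sees the survey; the form names only a study team member. Arm knowledge is possible, not certain.
- **The figures.** SD, alpha and shift are all assumed. The two-sample test is not the one named as primary, although the hypothesis in 12.1.1 does compare patients with and without a device. At a shift of 0.25 mmHg, the two-sample rate is close to nominal. The figures show sensitivity and are not evidence that bias will occur.
- **The remedy.** Reordering cannot mask a provider-investigator who already knows the assignment. Section 11.2 also allows study data to go into the medical record, which is another route. This stands, and it limits what the fix can claim.

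**Conclusion.** The point holds as a gap in procedure: the follow-up reading of the primary endpoint has no safeguard against knowledge of the arm, while the baseline reading is protected by its timing. The documents do not support saying that the reader will know the arm, or that a biased result is to be expected.

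The size is unknown. Under the stated assumptions, the effect on the false-positive rate runs from almost none for a 0.25 mmHg shift to about 27% for 1.5 mmHg in the 30 v 10 comparison. It is larger for the paired test in the pooled device patients, at about 42% for a 1 mmHg shift. The change is worth making because it is cheap and bears on the primary endpoint, although it gives only partial masking.

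**What to change.** In 9.3.2, state three things:
1. IOP is measured and recorded before the survey is given and before the drop aid is shown.
2. The drop aid stays out of sight until that reading is recorded.
3. Clinic staff who take IOP are not told the assignment, where existing staffing allows.

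Amend the footer of the diary form (15.2.3) to match, so that the patient shows the device to research staff only after the pressure check.

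The cost is protocol and form wording and a set order of steps at one visit. It needs no added visits, patients or staff. The downside is that masking stays incomplete: patients may mention their device, and a provider who is an investigator may already know the arm. The trial report should state that limit.

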## 9.4 Early Termination Visit

The subject can be terminated early from the study if there is a change in eye medication as determined by their SOC provider. Subjects can also be withdrawn from the study if they demonstrate non-compliance for study procedures.

#### 9.5 Non-Study Visits (Unscheduled Visits)

At non-study visits a standard office ophthalmology exam will be completed.

Reference Appendix section 15.1 for schedule of events.

Reference Appendix section 15.2 for complete CRF used for all study visits which include patient satisfaction survey and study diary.

## 10 Assessment of Safety and Data Safety Monitoring Plan (DSMP)

### 10.1 Definitions

The following definitions will be used in the assessment of safety:

*Adverse Event (AE)* is any untoward or unfavorable medical occurrence in a human subject, including any abnormal sign (for example, abnormal physical exam or laboratory finding), symptom, or disease, temporally associated with the subject's participation in the research, whether or not considered related to the subject's participation in the research.

*Serious Adverse Event (SAE)* is any adverse event that

- (1) results in death;
- (2) is life-threatening;
- (3) results in inpatient hospitalization or prolongation of existing hospitalization;
- (4) results in a persistent or significant disability/incapacity;
- (5) results in a congenital anomaly/birth defect; or
- (6) based upon appropriate medical judgment, may jeopardize the subject's health and may require medical or surgical intervention to prevent one of the other outcomes listed in this definition (examples of such events include allergic bronchospasm requiring intensive treatment in the emergency room or at home, blood dyscrasias or convulsions that do not result in inpatient hospitalization, or the development of drug dependency or drug abuse).

*Life-threatening* means that the event places the subject at immediate risk of death from the event as it occurred.

*Unanticipated Problem* is defined as an event, experience or outcome that meets **all three** of the following criteria:

- is unexpected; AND
- is related or possibly related to participation in the research; AND
- suggests that the research places subjects or others at a greater risk of harm (including physical, psychological, economic, or social harm) than was previously known or recognized.

*Possibly related* means there is a reasonable possibility that the incident, experience, or outcome may have been caused by the procedures involved in the research

*Unexpected* means the nature, severity, or frequency of the event is not consistent with either:

- the known or foreseeable risk of adverse events associated with the procedures involved in the research that are described in (a) the protocol–related documents, such as the IRB-approved research protocol, any applicable investigator brochure, and the current IRB-approved informed consent document, and (b) other relevant sources of information, such as product labeling and package inserts; or
- the expected natural progression of any underlying disease, disorder, or condition of the subject(s) experiencing the adverse event and the subject’s predisposing risk factor profile for the adverse event.

## 10.2 Safety Review

Both the risks listed in Section 6.1 and unknown risks will be monitored throughout this minimal risk study. The PI will have overall responsibility for the study. The PI will review all AEs, SAEs, and UPs. During the review, the PI will complete the form designated in Appendix 15.4.1 in which the AE will be graded and the relatedness will be determined. All SAEs and UPs will be promptly reported to the BUMC IRB as designated in Section 10.3. The SAE Report demonstrated in Appendix Section 15.4.2 will be completed for all SAEs and UPs.

[name] is the PI and will be responsible for the study. [name] will be notified within 1 week of any events determined an AE or SAE and 2 days of any event determined a UP. [name] will review all AEs/SAEs within 2 weeks and all UPs within 5 days. After this review, any recommended changes will be made to the PI and the co-investigators in addition to the BUMC IRB as deemed necessary by the PI.

Reference Appendix section 15.4 for all AE, SAE, and UP tracking and report examples.

## 10.3 Reporting Plans

The Principal Investigator at BMC/BU Medical Campus will report Unanticipated Problems, safety monitors’ reports, and Adverse Events to the BMC/BU Medical Center IRB in accordance with IRB policies:

- Unanticipated Problems occurring at BMC/BU Medical Campus involving a fatal or life-threatening event will be reported to the IRB within 2 days of the investigator learning of the event.
- Unanticipated Problems occurring at BMC/BU Medical Campus not involving a fatal or life-threatening event will be reported to the IRB within 7 days of the investigator learning of the event.
- Reports from safety monitors with recommended changes will be reported to the IRB within 7 days of the investigator receiving the report.
- Adverse Events (including Serious Adverse Events) will be reported in summary at the time of continuing review, along with a statement that the pattern of adverse events, in total, does not suggest that the research places subjects or others at a greater risk of harm than was previously known.
- Reports from safety monitors with no recommended changes will be reported to the IRB at the time of continuing review.

## 10.4 Stopping Rules

A subject will be withdrawn from the study for any of the following reasons but are not limited to:

- Change to eye drop regimen as determined by their SOC provider

- Failure to comply with drop aid instructions
- SAE or UP resulting from the administered study device

The study will be stopped if the PI, [name], determines that the number of AEs, SAE, and/or UPs exceed that of SOC ocular procedures.

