## 12 Statistical Plan

### 12.1 Study Hypotheses

#### 12.1.1. Primary Objective: Intraocular Pressure

Formal hypothesis: Drop aids will be cost-effective in delivery of ophthalmic medications by improving baseline IOP measures to six week visit.

Testable hypothesis: Patient baseline IOP measures will be a statistically significant improvement in accordance to the usage of a drop aid device.

Null hypothesis: The patients, who are assigned to a drop aid device baseline IOP measures will not have a statistically significant change with the usage of a drop aid device when compared to patients not assigned to a drop aid device.

Alternate hypothesis: Patients not assigned to a drop aid device will result in larger significant change when compared to patients who are assigned to a drop aid device.

$$H_0: \mu_0 < \mu_d - \delta$$

$$H_A: \mu_0 \geq \mu_d - \delta$$

Where  $\mu_0$ , is the true mean IOP change from baseline to the six week visit without the drop aid device,  $\mu_d$  is the true mean IOP change from baseline to the six week visit with the drop aid device.

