### 12.3 Statistical Methods

A variety of statistical analysis will be used to analyze the results. A paired t-test will be the primary method of analysis. Any significant differences measured will be between the pre and post intervention, with the patient serving as their own control. However, the analysis will not be limited to a paired t-test and will also likely include ANOVA, chi-squared, p-value, linear regression, among others. Other outcomes such as length of time until completion of drops will also be measured and compared to no drop aid controls. Significant differences will be measured with similar statistical analysis as stated previously. Satisfaction of use will be measured with a survey and results will be averaged among those in the same cohort. Any significant differences will also be measured with similar statistical analysis stated previously.

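### Sections 9.4 and 10.4 disagree on withdrawal after a change in eye drops, and no rule secures or analyses those patients' IOP, so the primary IOP analysis can lose patients selectively

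*Combined protocol and SAP*

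**What the plan says.** Section 10.4 (Stopping Rules) opens with "A subject will be withdrawn from the study for any of the following reasons", and its first listed reason is "Change to eye drop regimen as determined by their SOC provider". Section 9.4 (Early Termination Visit) reads: "The subject can be terminated early from the study if there is a change in eye medication as determined by their SOC provider". Despite its heading, Section 9.4 lists no procedure to perform, and Table 1 in Section 15.1 has no early-termination column.

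Section 5 defines the outcome: "The primary endpoint is the comparison of baseline IOP measurement and follow-up IOP measurement". The follow-up value comes from the final visit, at least six weeks after enrolment, where "IOP and VA will be checked as part of SOC clinic visit" and participation then ends (Section 9.3.2). Between enrolment and that visit the only planned contact is a phone call at three weeks. Section 9.5 provides for unscheduled visits: "At non-study visits a standard office ophthalmology exam will be completed".

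On analysis, Section 12.3 states: "A paired t-test will be the primary method of analysis". The null hypothesis in Section 12.1.1 is instead a contrast between groups, "when compared to patients not assigned to a drop aid device". Section 12 defines no analysis population, no missing-data method and no rule for withdrawn patients.

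**The concern.** The plan gives two answers to the same event. Under Section 10.4 the patient must leave; under Section 9.4 someone may decide. The triggers also differ: an eye medication is a wider category than the eye drop regimen. No blinding is described, and Section 9.1 allows the patient's provider to be an investigator. Any discretion under Section 9.4 could therefore be exercised by someone who knows both the group and the IOP.

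A paired test needs two IOP values per patient. A patient withdrawn before the final visit has no planned second value. If some of these withdrawals follow a raised IOP, the patients lost are those whose IOP went up, and those who remain look better than the group as randomised. The pre/post test could then show a fall where none occurred. If the devices do work, more controls than device patients would be lost, and the measured device benefit would be too small.

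**Working it through.** **1. The passages side by side.** Obligation: mandatory in 10.4, permissive in 9.4. Trigger: eye drop regimen in 10.4, eye medication in 9.4. IOP at withdrawal: required in neither. Analysis of withdrawn patients: not addressed in Section 12.

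**2. Timing.** A change ordered at the final visit does no harm if the IOP taken there is kept. Only earlier changes matter, for example at an unscheduled visit or during a long wait for the appointment. Section 2 gives a six-week minimum and no maximum.

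**3. The plan's own figure.** 4 groups × 10 = 40, as Section 12.2 states. The number was set by budget; no SD, effect size or dropout rate is given. At an assumed withdrawal rate r, the expected number with follow-up is 40(1 − r), and the chance that a given group of ten loses at least one patient is 1 − (1 − r)^10:

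| r | expected with follow-up | chance a group loses at least one |
|---|---|---|
| 5% | 38 | 40% |
| 10% | 36 | 65% |
| 20% | 32 | 89% |
| 30% | 28 | 97% |

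**4. Size of the bias if changes follow IOP.** Every input here is an assumption: mean change μ = 0 (control) or −2 mmHg (device); SD of change σ = 3 or 4 mmHg; a share s of patients seen before the final visit; correlation ρ of 0.5 to 1 between interim and final change; removal if the interim change is at least c = 3 or 4 mmHg, or if IOP reaches 21 mmHg (baseline 17, SD 3.5). The triggers are modelling devices, not clinical rules.

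For a rise trigger, z = (c − μ)/σ, p = 1 − Φ(z), and the mean change among those retained is μ − sρσφ(z)/(1 − sp).

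*Worst case* (s = 1, ρ = 1, σ = 4, c = 3):
- Control: z = 0.75, σφ(z) = 1.2045, p = 0.2266. Mean = −1.2045/0.7734 = −1.56.
- Device: z = 1.25, σφ(z) = 0.7306, p = 0.1056. Mean = −2 − 0.7306/0.8944 = −2.82.
- Difference: 1.26 instead of 2.0 mmHg.

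*Half the patients seen early* (s = 0.5, otherwise the same):
- Control: −0.6023/(1 − 0.1133) = −0.68.
- Device: −2 − 0.3653/(1 − 0.0528) = −2.39.
- Difference: 1.71 mmHg.

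*Mild case* (s = 0.1, ρ = 0.5, σ = 3, c = 4):
- Control: −0.05 × 0.492/(1 − 0.0091) = −0.02.
- Device: −2 − 0.05 × 0.162/(1 − 0.0023) = −2.01.
- Difference: 1.98 mmHg.

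Over s = 0.1 to 0.5 and all three triggers, the difference is about 1.7 to 2.0 mmHg and the spurious control fall about 0.02 to 0.7 mmHg.

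A separate simulation (baseline 17, SD 4; regimen changed with probability 0.25 to 1 once an interim reading exceeds 21 mmHg; every patient having such a reading) gave differences of 1.60 to 1.97 mmHg and spurious falls of 0.07 to 1.16 mmHg.

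**5. No true effect.** Both groups then have the same μ and lose patients at the same rate. The between-group difference stays near zero while each group shows the same spurious fall.

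**6. The proposed substitution.** Using the pre-change reading gives a mean of μ + s(1 − ρ)σφ(z). With s = 0.5, ρ = 0.5, σ = 4, c = 3, the control mean is 0.25 × 1.2045 = +0.30 and the device mean is −2 + 0.25 × 0.7306 = −1.82. The difference is 2.12 mmHg. With ρ = 1 there is no bias. So the substitution errs in the other direction, and by less: +0.30 against −0.68 at worst for s = 0.5.

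**The case against.** A reader might infer that Section 10.4 cuts the primary endpoint off on its own outcome: that IOP drives regimen changes and that the affected patients are deleted. The documents support neither step. No passage gives a reason for changing the drops; intolerance or cost would trigger the same rule, and changes unrelated to IOP would cost precision without this bias. Nor does any passage say that data already collected are discarded. The medical record is a source document (Section 11.2), so a reading from an unscheduled visit may well exist. These objections stand. What they leave is a gap: nothing requires that reading to be captured or says how it is used.

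A reader might also quote a loss of a third or more of the device effect. That needs every patient to have an interim reading equal to the final one and every trigger to lead to removal. The plan schedules no clinic visit between enrolment and the final visit, so 1.3 mmHg (difference) and 1.6 mmHg (spurious fall) are worst cases, not a range to expect.

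Nor does the rule manufacture a device benefit in the between-group comparison, as step 5 shows. The false fall arises in the pre/post test, which Section 12.3 names as primary, so it still matters here.

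Finally, the pre-change reading may itself have been selected for being high. That is correct, and it is why a sensitivity analysis is needed.

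**Conclusion.** The conflict between 9.4 and 10.4 is certain from the text and must be reconciled. Also certain is that no IOP is required at early termination and that no rule covers the analysis of withdrawn patients. Selective loss from the primary analysis is a plausible consequence, not an established one. It requires that some changes follow IOP, that they occur before the final visit, and that those patients' readings are left out.

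If all three hold, the paired test is biased towards a fall and a true device effect is understated. The size is unknown because the documents give no SD, effect or rate of regimen change. The ranges in step 4 for 10 to 50% of patients seen early are the reasonable guide. This should be fixed, with medium confidence; it is a cheap improvement.

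**What to change.** - Use one wording for the rule in Sections 9.4 and 10.4. The sponsor decides which medication changes count and whether withdrawal is mandatory; clinical decisions about the regimen stay with the provider.
- State in Section 12.3 that a regimen change does not remove the patient's data. Take the last post-baseline IOP before the new regimen starts from the medical record, enter it as that patient's follow-up IOP, and analyse it in the assigned group. If no such reading exists, record the value as missing.
- Report the number of regimen changes by group, with the date of each substituted reading.
- Add a sensitivity analysis without the substituted readings.

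The cost is wording in three sections and one CRF line. Some substituted readings will be earlier than six weeks, and some may be selected for being high; the sensitivity analysis shows how much this matters. The rule should be set before follow-up readings accrue, because a withdrawn patient's IOP may not be recoverable later.
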